# 5.6.12 Instructions for the Subjects

Subjects will be instructed to avoid all prohibited medications, treatments, and activities, as described in Section 5.6.10. They will be instructed that the application of any facial products (eg, sunscreen, moisturizer, makeup) is prohibited during all study visits from 2 hours before the first assessment and until all assessments are complete.

Use of facial products is permitted on all other dosing days; however, the products must be removed before study drug application and may be re-applied no sooner than 20 minutes after study drug application.

If a subject routinely shaves his/her face, they will be instructed to use a consistent shaving habit as much as possible (eg, same time each day, use of same shaving products), and on study visit days they must shave at least 2 hours prior to the first assessment and refrain from shaving until all assessments are complete.

Allergan		06 Feb 2018
CMO-MA-MED-0530	Version 2	Page 26 of 59

When the patients arrive at the study center on Days 3, 31, and 56, they will be instructed to wait approximately 30 minutes for acclimation to the study site environment before any assessments are made.

For application of study drug, subjects will be instructed by the study staff and by an instructional video:

- 1. To apply the study cream at approximately the same time every day (in the morning).
- 2. To wash their hands before and after each application of study drug.
- 3. To dispense approximately a pea size amount of study drug in the palm of the hand or fingertip.
- 4. To dab the study drug onto each of the 5 areas of the face (ie, forehead, nose, each cheek, and chin).
- 5. To gently spread the study drug to cover their entire face (hairline to mandibular ridge and from ear to ear).
- 6. Care must be taken to avoid applying the study drug to the eyes, eyelids, scalp, neck, ears, and any membrane of the inner nose, mouth, lips, or open wounds.

Detailed subject instructions on study drug application will be provided to subjects. Subject instructions will include the statements "For Topical Use Only" and "Keep Out of Reach of Children." Subjects will be instructed on the proper storage of study drug and to keep it out of the reach of children. Subjects will be instructed to return all used and unused study drug containers to the site.

Twenty-four hours before each visit, subjects should avoid any foods, beverages, or activities that they know trigger an increase in their facial erythema. Subjects will be asked to recall any missed applications of study drug.

# 6 TIMING OF STUDY PROCEDURES

Subjects will provide written informed consent before any study-related procedures are performed. The planned schedule of study assessments are in Table 1. When the subjects arrive at the study center on Days 3, 31, and 56, they will be instructed to wait approximately 30 minutes for acclimation to the study site environment before any assessments are made.

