# **4 INTRODUCTION**

## 4.1 Background

Rosacea is primarily an adult condition, with onset of symptoms generally occurring after the age of 30, often having a deep impact on a patient's self-esteem and quality of life. The diagnosis of rosacea is made based on the presence of 1 or more primary features centrally distributed on the face, including flushing (transient erythema), persistent (nontransient) erythema, papules and pustules, and/or telangiectasia. Persistent redness is the most common individual sign of rosacea and is defined as stable central facial erythema that is not transient flushing or blushing. Various secondary features may also be present including burning or stinging, plaque, dry appearance, edema, phymatous changes, and ocular manifestations. For many individuals with rosacea, symptoms are triggered or exacerbated by external stimuli leading to the theory that the vasodilation and immune dysregulation seen in rosacea is neurogenic in nature. Rosacea is not curable, and it generally requires long-term treatment to alleviate symptoms and delay or prevent disease progression. Rosacea has been classified into 4 standard subtypes, reflecting common patterns of signs and symptoms. Many patients may experience characteristics of more than one subtype at the same time, and these often may develop in succession. In many individuals with Subtype 1 rosacea (where persistent erythema is the predominant symptom), small blood vessels become visible on the skin. While rosacea may or may not evolve from one subtype to another, each individual sign or symptom may progress from mild to moderate to severe. Early diagnosis and treatment are therefore recommended.

Moderately effective topical treatments such as sulfonamides, metronidazole, azelaic acid, and oral tetracyclines are ineffective in managing persistent erythema associated with rosacea.

Alpha agonists have been approved for topical dermal application to reduce persistent erythema associated with rosacea. An  $\alpha$ 2-adrenoceptor agonist, brimonidine gel 0.33%, received United States Food and Drug Administration (US FDA) approval in 2013 for use in facial erythema of rosacea; however, it has been fraught with tolerability issues.

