# 5.6.10.3 Prohibited Activities

Twenty-four hours before all study visits, the following activities are prohibited:

- 1. Consumption of any food, alcohol, or other beverage that the subject knows increases their facial erythema.
- 2. Use of saunas, steam rooms, and hot tubs, or any other activities that the subject knows will increase their facial erythema.

During all study visits, application of any facial products (eg, sunscreen, moisturizer, makeup) is prohibited from 2 hours before the first assessment until all assessments are complete. Facial cleansers are allowed; however, application of study drug and study assessments should occur at least 20 minutes after the cleanser is used.

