# 6.1.2 Baseline Visit (Day 1)

The Day 1 Baseline Visit will take place up to 14 days after the Screening Visit. The screening and Day 1 baseline assessments may be performed on the same day. The following procedures will be performed at the Day 1 Baseline Visit (at the timepoints indicated in Table 1):

- Reconfirm inclusion/exclusion criteria.\*
- Record any AEs/TEAEs and changes in concomitant medication or concomitant procedures.
- Collect updated medical history.\*
- Vital sign measurement (blood pressure, pulse rate, oral body temperature).
- Urine pregnancy test (for women of childbearing potential only).\*
- CTA.
- Energy-Based Therapy (KTP, PDL, or IPL).
- Standardized photography of treatment area.
- CEA.
- Dermal Tolerability Assessment (investigator and subject).
- Items from Satisfaction Assessment for Rosacea Facial Redness.\*
- FACE-Q Satisfaction with Skin Scale.\*

\* only performed if screening and baseline assessments performed on separate visits.

# 6.1.3 Day 3

The subject will return to the site on Day 3 and the following procedures will be performed (at the timepoints indicated in Table 1):

- Record any AEs/TEAEs and changes in concomitant medication or concomitant procedures.
- Vital sign measurement (blood pressure, pulse rate, oral body temperature).
- CTA.
- Standardized photography of treatment area.
- CEA.
- Dermal Tolerability Assessment (investigator and subject).
- Items from Satisfaction Assessment for Rosacea Facial Redness.
- · Application and dispensing/collection of study drug.

The subject will be instructed how to apply the study drug at this visit and will be given a sufficient supply to enable once-daily application from Day 4 until Day 27. The subject will be instructed not to apply study drug on Day 28, Day 29, and Day 30.

#### 6.1.4 Day 29

The subject will return to the site on Day 29 and the following procedures will be performed (at the timepoints indicated in Table 1):

- Record any AEs/TEAEs and changes in concomitant medication or concomitant procedures.
- Vital sign measurement (blood pressure, pulse rate, oral body temperature).
- CTA.
- Standardized photography of treatment area.
- CEA.
- Dermal Tolerability Assessment (investigator and subject).
- Energy-Based Therapy (KTP, PDL, or IPL).
- FACE-Q Satisfaction with Skin Scale.

# 6.1.5 Day 31

The subject will return to the site on Day 31 and the following procedures will be performed (at the timepoints indicated in Table 1):

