# 8 STATISTICAL METHODS

#### 8.1 General Statistical Considerations

A brief summary of the general statistical analysis methods is provided below; full details will be provided in a separate statistical analysis plan, which will be finalized prior to database lock.

Data will be summarized using descriptive statistics (number of observations [n], mean, standard deviation, median, minimum, and maximum for continuous variables; and n and percentage for categorical variables).

Two critical timepoints, baseline and end of study, will be referenced in most of statistical analyses for this study. Baseline is defined as the latest assessment prior to any study treatments for each subject (Day 1). End of study is the last clinical visit an enrolled subject has in this study (Day 56 exit visit). Subjects who discontinue will be asked to return for the last clinical visit (Day 56 exit visit) for end-of-study data collection.

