# 8.1.3 Efficacy Variables and Analysis

The efficacy variables are:

- The number and percentage of subjects with at least a 1-grade decrease (improvement) on the CEA, from baseline over a 6-hour period following study drug application at each study visit and timepoint (specified in Table 1).
- Percentage change from baseline at each visit in rosacea facial redness using DIA of standardized facial photographs.
- Proportion of subjects indicating Satisfied or Very Satisfied (score of 3 or 4) with treatment on the Items from Subject Satisfaction Assessment for Rosacea Facial Redness and proportion of subjects indicating Somewhat Satisfied and Very Satisfied with treatment on the FACE-Q Satisfaction with Skin Scale at each visit and timepoint specified in Table 1.

The proportion of subjects with at least a 1-grade decrease (improvement) on the CEA from baseline (ie, predose on Day 1) will be summarized by visit and timepoint using frequency distributions. In addition, the raw CEA data will be summarized by visit and timepoint using descriptive statistics. Each item from the PROs (Items from Subject Satisfaction Assessment for Rosacea Facial Redness and FACE-Q Satisfaction with Skin Scale) will be summarized using frequency distributions by visit and timepoint.

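### Acclimation is required before erythema readings on Days 3, 31 and 56 but not on Day 1, whose single pretreatment reading is the baseline they are compared with

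*Protocol*

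**What the plan says.** Two places in the protocol set an acclimation rule, and they agree. Section 6 states that "on Days 3, 31, and 56, they will be instructed to wait approximately 30 minutes for acclimation" before assessments begin. Section 5.6.12 has the same rule: "When the patients arrive at the study center on Days 3, 31, and 56, they will be instructed to wait approximately 30 minutes". Neither names Day 1 or Day 29.

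Section 8.1.3 fixes the reference for the erythema response: the proportion with at least a 1-grade decrease "on the CEA from baseline (ie, predose on Day 1) will be summarized by visit and timepoint". Inclusion criterion 4 (Section 5.5.2) uses the CEA at baseline, grade 3 or more, to establish moderate to severe persistent erythema.

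On same-day visits, Section 6.1.2 says: "The screening and Day 1 baseline assessments may be performed on the same day". On triggers, Section 5.6.10.3 says: "Twenty-four hours before all study visits, the following activities are prohibited". The background in Section 4.1 notes that in many individuals "symptoms are triggered or exacerbated by external stimuli", and it separates persistent erythema from transient flushing.

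**The concern.** A change score is only as clean as the two readings behind it. The protocol asks subjects to settle before the later readings but not before the one reading that all of them are measured against. Redness that would fade during half an hour indoors could stay in the baseline and be absent later.

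If that happened in some subjects, two things would follow. The 1-grade improvement rate and the percentage fall in DIA redness on Days 3, 31 and 56 would include some recovery from arrival conditions. And some subjects could enter with a grade 3 that is partly transient, although the study is meant to follow persistent erythema. In a single-arm study no control group shares the artefact, so it would not cancel out of the change from Day 1.

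**Working it through.** The plan gives no figure to reproduce. The check is a comparison of the visit rules, followed by one labelled illustration.

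**Step 1. Visits side by side** (acclimation from Sections 5.6.12 and 6; reading times from Table 1 and its footnotes).

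| Visit | Acclimation required | CEA and photographs | Role |
|---|---|---|---|
| Screening | no | none | none for CEA or DIA |
| Day 1 | no | pretreatment, 1 h | entry CEA; baseline for CEA and DIA |
| Day 3 | yes | predose, 1, 3, 6 h | post-drug readings |
| Day 29 | no | pretreatment, 1 h | second energy session, no drug |
| Day 31 | yes | predose, 1, 3, 6 h | post-drug readings |
| Day 56 | yes | predose, 1, 3, 6 h | post-drug readings |

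The CEA endpoint in Section 5.2 is read at hours 1, 3 and 6 after study drug. Drug is applied on site only on Days 3, 31 and 56. So all nine scheduled post-drug readings (3 visits x 3 times) come from acclimated visits, and all are compared with Day 1.

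**Step 2. How many readings form the baseline.** One. Neither CEA nor photography is scheduled at screening. SAP Section 2.3.2 lists the parameters with repeated pretreatment values, and CEA and DIA are not among them; for the rest the single value is used. No second reading dilutes an unsettled one.

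**Step 3. Minimum time on site before a reading.** On Days 3, 31 and 56 the earliest post-drug reading follows a wait of about 30 minutes plus at least 60 - 15 = 45 minutes after application, so about 30 + 45 = 75 minutes. On Day 1 no minimum is stated. The 90-minute rule in Section 6.3 limits how long before energy treatment the reading may be taken; it does not require a wait after arrival.

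**Step 4. Controls that do cover Day 1.** The 24-hour trigger limit, the 2-hour facial-product limit (both Section 5.6.10.3) and consistent lighting for CEA (Section 7.1.1.1) apply at every visit. None is a settling period, and the protocol asks for the wait in addition to them on Days 3, 31 and 56.

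**Step 5. Same-day screening and Day 1.** The 24-hour limit still applies, but no earlier study visit exists at which the protocol has the instruction given. The 2-hour product limit can be met on the day by removing products and waiting.

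**Step 6. Illustration of size.** Assume that a share s of the enrolled subjects has one CEA grade added at baseline only, with no true change and no other error, and that all 45 are observed. Expected false responders at an acclimated visit = 45 x s:

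- s = 0.05: 45 x 0.05 = 2.25
- s = 0.10: 45 x 0.10 = 4.5
- s = 0.20: 45 x 0.20 = 9

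The values of s are assumptions. Nothing in the documents supports one over another, and s could be close to zero.

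**The case against.** The strongest case against has four parts.

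First, CEA and DIA are exploratory, and SAP Section 5.2 plans no efficacy hypothesis test. This stands: no test, power or sample size figure changes.

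Second, there are partial safeguards. Trained investigators are asked to grade persistent erythema, and same-day screening may well add time on site before the CEA. This stands in part. Appendix 14.1 has the clinician grade what is present at the time of evaluation, and any extra time on site is incidental.

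Third, CEA is summarised by visit and timepoint, so the settled predose readings on Days 3, 31 and 56 can be set against hours 1, 3 and 6 of the same visit. This also stands, but it answers a narrower question: the effect of that application, not the change since before any treatment.

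Fourth, Section 7.1.1.4 refers photography procedures to a Study Manual that is not among the documents. Whether it sets a wait for the baseline photographs cannot be known here.

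A reader might also infer more than the documents support:

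- That every later visit is affected. Day 29 has no acclimation either, so its pretreatment reading is like for like with Day 1.
- That the bias can only run towards improvement. The protocol gives the purpose only as adjusting to the site environment. That transient redness at baseline would favour improvement is sound reasoning, but how often subjects arrive redder, or paler, is not stated.
- That subjects screened and treated on one day cannot comply with the limits before baseline. The limits cover all visits, the product limit can be met that day, and trigger advice could be given before the visit.
- That the primary safety endpoints are compromised. Dermal tolerability also has a Day 1 baseline, but nothing in the documents shows that its scores, adverse events or CTA shift with arrival conditions.

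**Conclusion.** The point holds as an avoidable difference in measurement conditions. The protocol requires settling before the post-drug CEA readings on Days 3, 31 and 56 and does not require it before the single Day 1 reading that serves as entry grade and baseline. The facts are exact and no passage contradicts them.

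The consequence is conditional. If some subjects arrive on Day 1 with transient redness, improvement on Days 3, 31 and 56 is overstated and some grade 3 entries may be partly transient. The size is unknown; the range of 2.25 to 9 subjects in 45 rests wholly on the assumed 5% to 20%. The finding describes what the protocol requires, not what sites did: a site could have let subjects settle on Day 1 unasked. It deserves correction because change from Day 1 is the main efficacy evidence in a study without a control arm, and because the correction is small.

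**What to change.** In protocol Sections 5.6.12 and 6, replace the list Days 3, 31 and 56 with Days 1, 3, 29, 31 and 56, so that the entry and baseline readings and the Day 29 pretreatment readings follow the same rule as the rest. If the difference is deliberate, give the reason.

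Where screening and Day 1 fall on the same day, add an eCRF item, completed before the baseline CEA, recording whether the Section 5.6.10.3 limits were met.

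If the data are already collected, state the limitation in the report. Beside change from Day 1, also show CEA and DIA change from the same-visit predose reading on Days 3, 31 and 56, described as the within-visit effect of the application.

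Cost: about 30 minutes of waiting at each of two visits and one eCRF item. The additional summary uses readings already scheduled.

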# 6.1 Pretreatment

# 6.1.1 Screening Visit (Day -14 to Day -1)

During the screening visit the following assessments will be performed:

- Obtain informed consent.
- Assess for eligibility (against inclusion and exclusion criteria).
- Record demographic data, such as ethnic origin, date of birth, and sex.
- Collect full medical history.
- Record any AEs and concomitant medications or procedures.
- Perform a physical examination.
- Vital sign measurement (blood pressure, pulse rate, oral body temperature).
- Urine pregnancy test (for women of childbearing potential only).

- CTA.
- Fitzpatrick Skin Phototype.
- Items from Satisfaction Assessment for Rosacea Facial Redness.
- FACE-Q Satisfaction with Skin Scale.

# 6.1.2 Baseline Visit (Day 1)

The Day 1 Baseline Visit will take place up to 14 days after the Screening Visit. The screening and Day 1 baseline assessments may be performed on the same day. The following procedures will be performed at the Day 1 Baseline Visit (at the timepoints indicated in Table 1):

- Reconfirm inclusion/exclusion criteria.\*
- Record any AEs/TEAEs and changes in concomitant medication or concomitant procedures.
- Collect updated medical history.\*
- Vital sign measurement (blood pressure, pulse rate, oral body temperature).
- Urine pregnancy test (for women of childbearing potential only).\*
- CTA.
- Energy-Based Therapy (KTP, PDL, or IPL).
- Standardized photography of treatment area.
- CEA.
- Dermal Tolerability Assessment (investigator and subject).
- Items from Satisfaction Assessment for Rosacea Facial Redness.\*
- FACE-Q Satisfaction with Skin Scale.\*

\* only performed if screening and baseline assessments performed on separate visits.

# 6.1.3 Day 3

The subject will return to the site on Day 3 and the following procedures will be performed (at the timepoints indicated in Table 1):

- Record any AEs/TEAEs and changes in concomitant medication or concomitant procedures.
- Vital sign measurement (blood pressure, pulse rate, oral body temperature).
- CTA.
- Standardized photography of treatment area.
- CEA.
- Dermal Tolerability Assessment (investigator and subject).
- Items from Satisfaction Assessment for Rosacea Facial Redness.
- · Application and dispensing/collection of study drug.

The subject will be instructed how to apply the study drug at this visit and will be given a sufficient supply to enable once-daily application from Day 4 until Day 27. The subject will be instructed not to apply study drug on Day 28, Day 29, and Day 30.

#### 6.1.4 Day 29

The subject will return to the site on Day 29 and the following procedures will be performed (at the timepoints indicated in Table 1):

- Record any AEs/TEAEs and changes in concomitant medication or concomitant procedures.
- Vital sign measurement (blood pressure, pulse rate, oral body temperature).
- CTA.
- Standardized photography of treatment area.
- CEA.
- Dermal Tolerability Assessment (investigator and subject).
- Energy-Based Therapy (KTP, PDL, or IPL).
- FACE-Q Satisfaction with Skin Scale.

# 6.1.5 Day 31

The subject will return to the site on Day 31 and the following procedures will be performed (at the timepoints indicated in Table 1):

- Record any AEs/TEAEs and changes in concomitant medication or concomitant procedures.
- Vital sign measurement (blood pressure, pulse rate, oral body temperature).
- CTA.
- Standardized photography of treatment area.
- CEA.
- Dermal Tolerability Assessment (investigator and subject).
- Items from Satisfaction Assessment for Rosacea Facial Redness.
- Application and dispensing/collection of study drug.

The subject will be given sufficient study drug to enable once-daily application from Day 32 to the Day 56 exit visit.

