#### Treatment:

All subjects will receive one of the following energy-based therapies: Potassium Titanyl Phosphate [KTP], Pulsed Dye Laser [PDL], or Intense Pulsed Light [IPL] twice during the study (Day 1 and Day 29). Once-daily application of oxymetazoline HCl cream 1.0% will be initiated on Day 3 and continued until Day 56. Subjects will be washed out from study drug 24 hours prior to the energy-based therapy session on Day 29 and will recommence study drug administration on Day 31.

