# 4.5 Rationale for Study Design

Oxymetazoline has been shown in 3 pivotal Phase 3 studies to be effective in treating persistent facial erythema in subjects with rosacea. Energy-based therapies have also been seen to be efficacious in reducing erythema and telangiectasia in rosacea patients. This Phase 4 study is the first to investigate the safety, tolerability, and preliminary measurements of oxymetazoline HCl cream 1.0% when used as an adjunctive treatment to energy-based therapy (ie, KTP, IPL, and PDL) for patients with moderate to severe persistent facial erythema associated with rosacea.

The side effects of energy-based therapy can include transient pupura and immediate posttreatment erythema, which normally resolve within a day or 2. In a recent publication, energybased therapy was performed the same day as Mirvaso® application for the treatment of rosacea with no safety concerns reported related to concurrent treatment. As an additional safety precaution we are delaying oxymetazoline treatment for 48 hours post energy-based therapy (and 24 hours prior to re-treatment with energy-based device) to limit any potential interaction between the device and drug. Any potential AEs that may arise from the use of a device will be noticeable within a 48-hour window, which will alert the physician as to whether oxymetazoline treatment should be applied.

There are 6 safety determinations in the current study (adverse events, urine pregnancy in females of childbearing potential, physical examination, vital signs, Clinician's Telangiectasia Assessment [CTA], and Dermal Tolerability Assessment). Four assessments will be used as measures of efficacy: Clinician Erythema Assessment [CEA], Items from Satisfaction Assessment for Rosacea Facial Redness, FACE-Q Satisfaction with Skin Scale, and Digital Image Analysis [DIA] of standardized photography of the treatment area).

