## **Investigational Plan**

### 5.3 Overall Study Design and Plan: Description

This is a Phase 4, multicenter, interventional, open-label study to evaluate the safety and tolerability of once-daily oxymetazoline HCl 1.0% cream when used as an adjunctive treatment to energy-based therapy for subjects with moderate to severe facial erythema associated with rosacea. The study will enroll approximately 45 subjects at 4 study centers within the United States.

All subjects will receive 1 of the following energy-based therapies (Potassium Titanyl Phosphate [KTP], Pulsed Dye Laser [PDL] or Intense Pulsed Light [IPL]) on Day 1 and Day 29 of the treatment period. Once-daily application of oxymetazoline HCl cream 1.0% will be initiated on Day 3 of the treatment period and will continue until the final exit visit (excluding a 3-day washout period that begins 24 hours prior to the second energy-based therapy session on Day 29).

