# 06 Feb 2018

Version 2

Page 18 of 59

Study Period	Screening*	Day 1/ Baseline*	Day 3	Day 29	Day 31	Day 56/ Exit Visit
Visit Window	Day -14 to Day -1	N/A	N/A	± 3 Days	+2 days from Day 29	± 3 Days
Informed Consent	Х					
Demographics	Х					
Fitzpatrick Skin Phototype	Х					
Inclusion/Exclusion Criteria	Х	X a				
Medical History	Х	X b				
Physical Examination	Х					Х
Vital Sign Measurement	Х	X a	Xc	X a	X c	Х
Urine Pregnancy Test (if applicable)	Х	X a,b				Х
Energy-Based Therapy (KTP, PDL, or IPL)		Х		Х		
Onsite Study Drug Treatment/Dispensing			Х		Х	X d
Standardized Photography		X e	X f	X e	X f	X f
Clinician Erythema Assessment (CEA)		X e	$\mathbf{X}^{\mathbf{f}}$	X e	Xf	X f
Clinician's Telangiectasia Assessment (CTA)	X	X a,b	X a	X a	X a	X a
Items From Satisfaction Assessment for Rosacea Facial Redness	Х	X a,b	X g		X g	X g
FACE-Q Satisfaction With Skin Scale	Х	X a,b		X a		X a
Dermal Tolerability Assessment (Investigator and Subject)		X e	$X^h$	X e	X h	X h
Adverse Events/Reactions	۹					
Concomitant Medications and Concurrent Procedures	◀					

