# 5.6.7 Selection and Timing of Energy Therapy

Laser and light therapy have been shown to reduce erythema and telangiectasia in patients with rosacea. Subjects will be allocated to one of KTP, PDL, or IPL treatments and undergo 2 sessions (Day 1 and Day 29) during the study. The 28-day period between the 2 treatments is standard in current practice allowing for efficacious results.

Subjects will begin study drug administration on Day 3 (2 days after the first energy-based therapy session) and will washout study drug from 24 hours prior to the second energy-based therapy session on Day 29, until 2 days after (Day 31). This will ensure that the study drug will not be present on the skin during the energy-based therapy or during the immediate recovery period during which there may be irritation to the skin. Any post-treatment skin irritation will be identified by the physician during this washout period and oxymetazoline treatment will not recommence until deemed safe to do so.

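### Subjects are to be told to stop the cream on fixed Days 28 to 30, but the second energy session may fall as early as Day 26, which would leave a home dose about 24 hours after it instead of 48 (low severity)

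*Protocol*

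**What the plan says.** **The rule is relative to the session.** The protocol synopsis (Treatment) has subjects "washed out from study drug 24 hours prior to the energy-based therapy session on Day 29". Section 5.3 excludes from dosing "a 3-day washout period that begins 24 hours prior to the second energy-based therapy session on Day 29". The rationale in 4.5 reads "we are delaying oxymetazoline treatment for 48 hours post energy-based therapy (and 24 hours prior to re-treatment with energy-based device"). Section 5.6.7 says subjects "will washout study drug from 24 hours prior to the second energy-based therapy session on Day 29, until 2 days after (Day 31").

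**The session can move, and the restart visit moves with it.** The visit-window row of Table 1 gives the Day 29 visit, which includes the second session, 3 days either way. The Day 31 visit is placed at plus "2 days from Day 29".

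**The instruction does not move.** At the Day 3 visit (6.1.3) the subject receives enough cream for Days 4 to 27, and the site is directed as follows: "The subject will be instructed not to apply study drug on Day 28, Day 29, and Day 30". Section 5.6.1 lists the same three days in brackets beside its session-relative clause. SAP 1.1.1 likewise has cream through Day 27 and the session on Day 29. Neither document says that the three days shift when the session shifts.

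**There is a control on restart.** After the session, section 5.6.7 says, "oxymetazoline treatment will not recommence until deemed safe to do so". Section 5.6.1 lets the investigator delay or stop the cream if the device has caused skin problems.

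**The concern.** A fixed instruction and a movable session agree only when the session falls on its nominal day. If the session comes early, a subject who follows the fixed days may still be applying cream inside the interval that the protocol wants kept clear.

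That interval has two stated purposes. The first is a safety check. Section 4.5 says "Any potential AEs that may arise from the use of a device will be noticeable within a 48-hour window", and the physician uses what is seen to decide whether cream should be applied. The second, in 5.6.1, is to keep device and drug apart in time so that a treatment-related event can be assigned to one or the other. A home dose within the 48 hours comes before the check and blurs the assignment. Attribution feeds the causality grading, which rests on timing relative to study drug, and the SAP 6.2 table of treatment-emergent events related to energy therapy and leading to discontinuation of the cream.

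Table 1 has no visit between Day 3 and the session at which the stop date could be corrected. The procedures listed for the session visit in 6.1.4 include no instruction about the cream.

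**Working it through.** **Inputs.** Home doses on Days 4 to 27 (6.1.3). Barred days 28, 29 and 30 (5.6.1, 6.1.3). Session day s from 29 − 3 = 26 to 29 + 3 = 32 (Table 1). Restart visit at s + 2 (Table 1). Doses on visit days are applied at the site (5.6.1), and Table 1 lists none at the Day 29 visit, so no dose is counted on day s. Dosing is in the morning; as an approximation, the session is taken at a similar clock time.

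**The plan's own case.** With s = 29, the next dose is on Day 31, and 24 × (31 − 29) = 48 hours. The fixed days reproduce the stated interval for an on-time session.

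**All permitted session days.** Hours before = 24 × (s − last home dose day). A home dose inside the 48 hours is one on day s + 1.

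| Session day | Last home dose before (hours) | Home dose on s + 1 | Restart visit | On a barred day? |
|---|---|---|---|---|
| 26 | Day 25 (24) | Day 27 | Day 28 | yes |
| 27 | Day 26 (24) | none | Day 29 | yes |
| 28 | Day 27 (24) | none | Day 30 | yes |
| 29 | Day 27 (48) | none | Day 31 | no |
| 30 | Day 27 (72) | none | Day 32 | no |
| 31 | Day 27 (96) | none | Day 33 | no |
| 32 | Day 27 (120) | none | Day 34 | no |

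- After the session: only s = 26 fails, with 24 × (27 − 26) = 24 hours against 48. The dose also precedes the Day 28 visit.
- Restart visit on a barred day: s = 26, 27 and 28, so 3 of 7.
- Before the session: about 24 hours for s = 26, 27 and 28, against a required 24.

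**Sensitivity to clock time.** The documents give no clock times. Assume cream at hour a = 7 to 10 and a session at hour t = 8 to 16. For s = 26, the gap after the session is 24 + (a − t), from 24 + 7 − 16 = 15 to 24 + 10 − 8 = 26 hours. It is short of 48 throughout. The gap before is 24 + (t − a), from 24 + 8 − 10 = 22 to 24 + 16 − 7 = 33 hours, which straddles 24.

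**With session-relative days.** The cream-free days become s − 1, s and s + 1, and the first dose is on s + 2. That gives 24 × 2 = 48 hours for every s from 26 to 32. For s = 26 the days are 25, 26 and 27, with restart on Day 28.

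**The case against.** The strongest reply is that Days 28 to 30 are nominal labels. Section 5.6.1 gives them as a gloss on a session-relative washout, and Table 1 uses Day 29 as a visit name. The literal reading would also put the on-site restart on a barred day for three permitted session days, which suggests it was not intended. That is probably what the authors meant. It does not remove the gap, because 6.1.3 specifies the instruction to be given and uses the nominal days without saying that they move.

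The controls also count. At every visit after Day 3 subjects are asked whether they applied the cream each morning, and breaches are recorded (5.6.11). Cream use is therefore discussed at a Day 26 session, a day before the only dose in question, and staff can correct the instruction then. A dose inside the interval would fit the protocol 8.3 item on significant departures from the dosing schedule, although the one example SAP 13 gives under that item concerns visits more than 7 days out of window. Section 4.5 calls the delay an extra precaution and cites a publication on same-day use of a related gel that raised no safety concern. These points stand, and they keep the severity low.

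A reader might infer that subjects receive only the fixed days, in writing. The documents do not show this: 6.1.3 directs the site, and 5.6.12 refers to separate detailed subject instructions that are not reproduced.

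**Conclusion.** The point holds as an inconsistency of low severity. Sections 5.6.1 and 6.1.3 fix the cream-free days, the rule is relative to the session, and the permitted window separates the two. Followed as written, 1 of 7 permitted session days (Day 26) leaves a home dose about 24 hours after the session instead of 48, before the next scheduled skin check. On 3 of 7 days (26, 27 and 28) the instruction conflicts with the restart visit. These are counts of days, not shares of subjects; the documents do not say how many sessions will be early. The result assumes that the subject follows the fixed days and that nobody corrects them.

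Three stronger readings are not supported:

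- **A breach before early sessions.** The gap is about 24 hours against a required 24. Whether it falls short depends on clock times that the documents do not give.
- **A problem with late sessions.** A subject could in principle resume on Day 31 before a late session or restart visit. However, the Day 3 supply is planned only to Day 27, and dosing resumes at the visit 2 days after the session, so no scheduled dose falls inside the interval.
- **An effect on the primary endpoints.** The counts of treatment-emergent events, dermal worsening and telangiectasia worsening do not depend on cause and do not change.

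What is weakened, slightly, is the stated safety precaution and drug-versus-device attribution.

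**What to change.** In protocol 5.6.1 and 6.1.3, define the cream-free days as the day before, the day of and the day after the actual second session, with restart at the visit 2 days after it. Days 28, 29 and 30 can stay as the example for an on-time session. Have the site confirm the stop date with the subject when the session is booked, since a correction at the session comes too late for the day before. The separate subject instructions and SAP 1.1.1 should follow the same wording.

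The supply sentence in 6.1.3 needs a matching adjustment. Under the session-relative rule, the last home dose before a Day 32 session would be on Day 30, 3 days beyond the Day 27 now provided for.

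The cost is one clause in each of two protocol sections, the consequential wording and one confirmation per subject. No extra visits, subjects, eCRF fields or SAP flags are needed.
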